7.4. Exposure and Compliance

Drug and placebo will be supplied in identical

Each spray delivers 1.6 μg per 100 μL spray. At Visit 2 (Baseline) and Visit 3

(Treatment), site personnel will instruct the subject to self-administer the IP by 1 spray into each nostril (right and left nasal passages), for 2 total sprays per dose; thus, 1 dose equals 2 sprays, or 3.2 μg. All vials dispensed at Visit 2 (Baseline) will contain placebo nasal spray solution.

Total number of doses of placebo and PH94B will be summarized by treatment group and subjects, by study visit for the Safety Population. Data will also be presented in a by-subject listing.

8. Efficacy Analysis

All efficacy analyses will be performed on the ITT Population (as defined in Section 5) unless otherwise noted. The order of testing for the primary and secondary endpoints is discussed in Section 6.1.3. Exploratory endpoints are not included in the testing strategy.

8.1. Primary Efficacy Analysis – Average Treatment SUDS Scores

The primary endpoint will be tested for the following hypothesis:

H₁₀: Mean change in average SUDS score from Visit 2 (Baseline) to Visit 3 (Treatment) does not differ between PH94B and placebo.

H₁₁: Mean change in average SUDS score from Visit 2 (Baseline) to Visit 3 (Treatment) does differ between PH94B and placebo.

The estimand for the primary efficacy endpoint has the following components:

Attribute	Definition
Treatment	The treatment of interest is PH94B, 3.2 µg administered as an intranasal solution (a 1.6 µg spray to each nostril per dose).
Population	The population of interest is adult subjects with SAD as defined by the protocol inclusion and exclusion criteria.
Variable of Interest	The variable of interest to be measured is the change from Visit 2 (Baseline) to Visit 3 (Treatment) in average SUDS score during a 5-minute public speaking challenge.
Intercurrent Events	Intercurrent events are expected to be rare. Any intercurrent event that does occur will be handled using the treatment policy strategy, i.e., included in the treatment regimen under evaluation.
Population Summary	The difference of means from Visit 2 (Baseline) to Visit 3 (Treatment) in SUDS will be estimated for each treatment group. PH94B will be compared to placebo using differences in LS group means.

8.1.1. ANCOVA Analysis of the Primary Endpoint

For each subject at each public speaking challenge, average SUDS scores and change from baseline (Visit 2 [Baseline] to Visit 3 [Treatment]) in average SUDS scores will be calculated as described in Section 6.1.7. Descriptive summaries of average SUDS scores and change from baseline in average SUDS scores will be provided for the primary endpoint based on the observed data.

An ANCOVA model will be used to test the null hypothesis that there is no difference in change from baseline average SUDS scores between PH94B- and placebo-treated subjects. Treatment group and analysis site will be included as factors and baseline average SUDS score as a covariate. The change from baseline LS means with standard error (SE), 95% CI for the LS means, *P* value for testing if the LS mean is 0, LS mean difference between treatment groups (PH94B minus placebo) with SE, 95% CI for the LS mean difference, and *P* value for testing if the treatment LS means are equal will be presented.

It is expected that all randomized study subjects will complete the Visit 3 (Treatment) assessments. If, for unanticipated reasons (intercurrent events), the fraction of subjects with missing change from baseline to Visit 3 (Treatment) average SUDS scores is greater than 0.05, change from baseline to Visit 3 (Treatment) average SUDS scores will be imputed using the fully conditional specification approach to multiple imputation as described in Section 6.1.4. If the fraction of missing change scores is ≤0.05, missing change from baseline to Visit 3 (Treatment) in average SUDS scores will be imputed with treatment group mean change scores.

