5.2.2 Phase 2 Studies

Two previously completed Phase 2 clinical studies have enrolled similar populations and had similar efficacy endpoints to Protocol PH94B-CL026. These double-blind, randomized, placebo-controlled Phase 2 clinical studies () included a total of

12-Aug-2022 Amendment 3, Version 4.0

AD-MW-07.08 18-Jun-2019

Protocol PH94B-CL032

91 female subjects who met criteria for SAD (generalized subtype) as defined by the Diagnostic and Statistical Manual of Mental Disorders, 4th Edition. PH94B (1.6 µg) was administered i.n. in spray form to both a performance (public speaking) challenge and a social interaction challenge simulation which took place at the clinical sites.

The primary outcome measures were the Clinical Global Impression Scale of Improvement (CGI-I) and the Subjective Units of Distress Scale (SUDS). The SUDS scores range from 0 to 100, with higher scores indicating greater levels of anxiety. Subjects receiving PH94B were more likely than those who received placebo to show improvement on the CGI-I following treatment. In the PH94B group, 34 of 45 subjects (75.6%) were rated very much less anxious or much less anxious compared to only 17 of 46 subjects (37%) in the placebo group. A test for the difference between proportions indicated a Z value of 4.03, p = 0.0001 (Fisher's exact test).

During the public speaking challenge, subjects randomized to PH94B (n=45) showed an improvement of 26.7 points in the mean score on the SUDS at Visit 3 (initial treatment visit) as compared to Visit 2 (baseline visit, at which all subjects received placebo). In comparison, subjects randomized to placebo (n=46) showed an improvement of only 14.0 in the mean SUDS score across visits. The PH94B group's improvement from Visit 2 to Visit 3 significantly exceeded the placebo group's improvement from Visit 2 to Visit 3 (t = 3.16, p = 0.002) on this challenge. No SAEs were reported, and no subjects were terminated prematurely from the study due to AEs.

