10.2.3 Visit 3 (Treatment): Public Speaking Challenge

At Visit 3, subjects should return to the study site and the following assessments will be completed:

- Measure vital signs after the subject has rested for 5 minutes: seated systolic and diastolic blood pressure, heart rate, respiratory rate, and body temperature
- Perform urine drug screen (Instant Exam, to be performed on site, with results documented in the source)
- For females of child-bearing potential, obtain urine sample and complete on-site urine pregnancy test
- Record concomitant medication use
- Review and record AEs
- Randomize the subject
- follow the instructions for the Visit 3 public speaking challenge (as described in Section 10.2.2 and Figure 10-1) with the same trained observer as in Visit 2; the subject will record SUDS accordingly

After the completion of the Visit 3 public speaking challenge:

- Complete the PGI-C (by the subject)
- Complete the CGI-I (by the trained observer of the public speaking challenge)
- Review and record AEs
- Administer C-SSRS (Since Last Visit) as the last part of the visit

The Follow-up visit (Visit 4) will be scheduled for 1 week ± 2 days after the date of Visit 3.

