3.2. Sample Size and Power

The sample size calculation was based on the similarly designed Phase 2 randomized, double-blind, placebo-controlled clinical study of PH94B with the primary outcome variable of average subjective anxiety based on SUDS scores.

AD-ST-33.06 Effective date: 12-Nov-2020

Version Final 1.0 | Date 28-Jun-2022 | AD-ST-33.06 Effective date: 12-Nov-2020 | Page 14 of 140

Because this Phase 3 study will involve 15 to 18 sites

Based on these considerations, 208 subjects (104 in each arm) will be included in the study.

Figure 1 provides the power curve used to determine the sample size.

An estimated 400 subjects will be screened to randomize 208 subjects in a 1:1 manner to either PH94B or placebo.

[figure not shown]

3.3. **Study Population**

The study population consists of male or female subjects, 18 through 65 years of age, inclusive, with a current diagnosis of SAD and with no prior or current conditions that would increase risk of treatment or confound the results of the study.

3.4. **Treatments Administered**

Subjects will be randomized 1:1 to receive one of the treatments listed below at Visit 3 (Treatment).

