4.1. Introduction

Data processing, tabulation of descriptive statistics, calculation of inferential statistics, and graphical representations will primarily use SAS (release 9.4 or higher). If the use of other

software is warranted, the final statistical methodology report will detail what software was used for what purposes.

Unless otherwise stated, all continuous (quantitative) variable summaries will be presented by treatment group and include the number of subjects with non-missing values (n), mean, SD, minimum, first quartile (Q1), median, third quartile (Q3), and maximum.

Unless otherwise stated, all categorical (qualitative) variable summaries will be presented by treatment group and include the frequency and percentage of subjects who are in the particular category or each possible value. In general, the denominator for the percentage calculation will be based upon the total number of subjects in the relevant study population with non-missing values.

The minimum and maximum will be reported with the same degree of precision (i.e., the same number of decimal places) as the observed data. Measures of location (mean, median, Q1, and Q3) will be reported to 1 degree of precision more than the observed data and measures of spread (SD) will be reported to 2 degrees of precision more than the observed data.

Percentages <100% will be presented to 1 decimal place and percentages of 100% will be reported with no decimal place. Counts of zero will be presented without percentages.

Unless otherwise indicated, all statistical tests will be conducted at the 0.05 significance level using 2-tailed tests, and *P* values will be reported. Corresponding 95% confidence intervals (CIs) will be presented for statistical tests.

To control for the overall type I error rate, a fixed-sequence testing strategy will be used. If statistical significance is declared for the primary endpoint, formal hypothesis testing will be done for the secondary endpoint. If a non-significant *P* value is reached for the primary endpoint, *P* values for the secondary endpoint will be considered exploratory. The *P* values from the exploratory endpoints are not included in the fixed-sequence testing strategy and are included for informational purposes only. The planned sequence of hypothesis testing is detailed in Section 6.1.3.

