6.1.4. Handling of Dropouts or Missing Data

Data will be included in the analysis according to the analysis visit windows described in Section 6.1.5.

It is expected that all study subjects who are randomized at Visit 3 (Treatment) will complete the Visit 3 (Treatment) public speaking challenge immediately after randomization and be included in the primary efficacy analysis. If a subject has incomplete scores during the 5-minute interval, then their average SUDS score will be calculated using the non-missing scores. If all public speaking challenge Visit 3 (Treatment) SUDS scores are missing for unanticipated reasons (intercurrent events) that arise during Visit 3 (Treatment), the average SUDS score will be set to missing. If the fraction of missing change from baseline to Visit 3 (Treatment) average SUDS scores in the ITT population is greater than 0.05, multiple imputation of the change from baseline to Visit 3 (Treatment) average SUDS scores will be carried out for the primary efficacy analysis. The fraction of missing average change from baseline in average SUDS scores will be computed as described in Section 6.1.7.2.

only change from baseline SUDS scores will be imputed. Other efficacy and safety data will not be imputed and will be analyzed as observed.

The imputation approach has 2 broad components: i) the multiple imputation process for the placebo and PH94B data; and ii) the analysis method that will be used to draw inference regarding the primary causal estimand, along with the method for combining the results across the multiply-imputed datasets. The primary causal estimand is defined in Section 8.1.

The imputation approach for the primary efficacy endpoint will be carried out in SAS using the fully conditional specification (FCS) method with a regression model (Carpenter and Kenward, 2013). The method assumes data are missing at random (MAR). Thus, subjects with missing values will have imputed values similar to other subjects with comparable observed profiles in the regression variables. The imputation will be carried out separately within each treatment group. The regression model will include the following variables: baseline SUDS score, sex, age, baseline LSAS total score, and analysis site. For each imputation process, a total of 25 complete datasets will be created. The random seeds to be used in the imputation steps are 157340717 and 127581968 for the PH94B and placebo arms, respectively.

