7.3. Demographics and Other Baseline Characteristics

Demographic variables will include race, ethnicity, age (based on date of informed consent), age categories (18-35 years, 36-55 years, 56-65 years), age at onset (from SAD Diagnostic Checklist), sex, height, weight, and body mass index (BMI).. Baseline variables will include average SUDS score at Visit 2 (Baseline), pre-IP SUDS score at Visit 2 (Baseline), average anticipatory SUDS score at Visit 2 (Baseline), and LSAS total score at Visit 1 (Screening).

Demographic and baseline characteristic data will be summarized for the Safety, ITT and PP Populations by treatment group (including subjects not randomized for the Safety population only) and overall subjects. Data will also be presented in a by-subject listing.

Medical and psychiatric history will be summarized for the Safety Population by treatment group and overall subjects, classified by system organ class (SOC) and preferred term. Data will also be presented in a by-subject listing, which will include SOC, preferred term, and the verbatim term.

Prior medications will be summarized by treatment group, subjects not randomized and overall subjects, by the number and percentage of subjects taking each medication and classified by ATC class and preferred term. This analysis will be conducted for the Safety population. Data will also be presented in a by-subject listing, which will include ATC Level 2 classification, preferred name, and verbatim name.

Results from the Mini-International Neuropsychiatric Interview (MINI) and SAD Diagnostic Checklist will be tabulated by treatment group, subjects not randomized and overall subjects for the Safety population and presented in a by-subject listing.

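### The primary ANCOVA adjusts only for analysis site and baseline average SUDS; pre-specifying screening LSAS total score, which is already collected, could add precision at almost no cost

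*SAP*

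**What the plan says.** SAP 8.1.1 gives the primary model: "Treatment group and analysis site will be included as factors and baseline average SUDS score as a covariate". SAP 6.1.2 sets the same limit for all planned ANCOVAs, and Protocol 13.1.4.2 names baseline SUDS as the only covariate.

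Other pre-randomisation values are collected. Beside the baseline average SUDS, SAP 7.3 lists "pre-IP SUDS score at Visit 2 (Baseline), average anticipatory SUDS score at Visit 2 (Baseline), and LSAS total score at Visit 1 (Screening". Protocol 8.2.1 requires an LSAS total of 70 or more at screening, so each eligible subject has one.

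SAP 6.1.4 specifies a multiple-imputation regression containing "baseline SUDS score, sex, age, baseline LSAS total score, and analysis site". It is used only when more than 5% of change scores are missing. The visible text gives no reason for leaving sex, age, LSAS or the other Visit 2 scores out of the test, and no figure for how well they predict the outcome.

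**The concern.** In a randomised comparison of means, adjusting for a pre-randomisation variable that predicts the outcome reduces the residual variance, and so the standard error of the treatment difference. Baseline average SUDS is measured at one challenge about a week before the outcome, and it is unlikely to carry all the predictive information available. LSAS is a separate, clinician-rated measure of severity. If it adds anything, the planned model leaves that precision unused although the data are already in hand.

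What is at stake is some power and some width of the confidence interval. The validity of the primary test is not affected: type I error, bias and the estimand are untouched.

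**Working it through.** **The plan's own figure.** SAP 3.2 says "Based on these considerations, 208 subjects (104 in each arm) will be included in the study" and "The sample size calculation was based on the similarly designed Phase 2 randomized, double-blind, placebo-controlled clinical study of PH94B". The target power, difference and SD cannot be read in the public text, so 208 cannot be reproduced. That is not an error in the plan.

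The Phase 2 results in Protocol 5.2.2 give some context:
- The PH94B group "showed an improvement of 26.7 points in the mean score on the SUDS at Visit 3", against 14.0 on placebo. The difference is 26.7 − 14.0 = 12.7, with t = 3.16 and n = 45 and 46.
- SD of change = 12.7 / (3.16 × √(1/45 + 1/46)) = 19.2.
- Per arm for 80% power, two-sided 0.05: 2 × (1.960 + 0.842)² × (19.2/12.7)² ≈ 36. For 90% it is 48.
- At 104 per arm, SE = 19.2 × √(2/104) ≈ 2.66, and the power for 12.7 points is 99.8%.
- At that SD, 104 per arm detects 7.4 points with 80% power or 8.6 points with 90%.

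So 208 must rest on a smaller effect, a larger SD, or both. The power of the current model is therefore taken as 80%, and alternatively 90%, as an assumption.

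**Inputs for the covariate check**
- Two-sided 0.05 (SAP 4.1: "all statistical tests will be conducted at the 0.05 significance level using 2-tailed tests").
- 208 subjects, 1:1.
- 18 sites, the top of the protocol's 15 to 18, with no pooling. Residual degrees of freedom = 208 − 1 (intercept) − 1 (treatment) − 17 (site) − 1 (baseline SUDS) = 188.
- R² is the share of the residual variance, after site and baseline average SUDS, that the added covariates explain. It is assumed, from 0 to 10%.

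**Gross effect.** SE ratio = √(1 − R²). Equivalent extra subjects = 208/(1 − R²) − 208. For R² of 2, 5 and 10% the SE falls by 1.0, 2.5 and 5.1%, worth 4.2, 10.9 and 23.1 subjects.

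**Net of the degrees of freedom.** With k added covariates the variance is multiplied by (1 − R²) × (1 + k/(188 − k)). Power comes from a noncentral t with 188 − k degrees of freedom. The noncentrality is set so that the current model has exactly 80% (value 2.816) or 90% (value 3.258), then divided by the square root of that factor.

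| Assumed added R² | One covariate, from 80% | Two covariates, from 80% | Two covariates, from 90% | Net equivalent subjects, two covariates |
|---|---|---|---|---|
| 0% | 79.8% | 79.6% | 89.7% | −2.2 |
| 2% | 80.6% | 80.4% | 90.3% | +2.0 |
| 5% | 81.8% | 81.6% | 91.1% | +8.6 |
| 10% | 83.8% | 83.6% | 92.5% | +20.7 |

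**Break-even.** Setting (1 − R²)(1 + k/(188 − k)) = 1 gives R² = k/188, which is 0.5% for one covariate and 1.1% for two.

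**Which values are eligible.** Screening LSAS and the Visit 2 pre-dose SUDS precede randomisation. The Visit 2 anticipatory SUDS follows the Visit 2 dose, but SAP 7.4 says all Visit 2 vials hold placebo, so it too is a legitimate covariate. Visit 3 scores differ. Protocol 10.2.3 runs the Visit 3 challenge "as described in Section 10.2.2 and Figure 10-1", and that figure is not shown. Protocol 7.1 places Visit 3 SUDS collection ahead of the speech, while Protocol 9.2 places dosing twenty minutes ahead of it. A score taken before the challenge can therefore be a score taken after the randomised dose.

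**The case against.** The strongest objection is that nothing in the documents shows these values to be prognostic once site and baseline average SUDS are in the model. That stands. Entry rules also narrow the useful range: LSAS is truncated at 70, and SAP 3.5 requires at least one Visit 2 SUDS rating of 75 or more. The outcome is not a single rating either. It is an average of scores taken each minute, analysed as change with baseline adjustment, which already removes some noise. Adjusting for the stratification factor and the endpoint's baseline is a standard, valid choice.

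The objection that the change costs more than wording holds only in part. A subject lacking an added covariate would drop out of the ANCOVA, and a covariate absent from the imputation model would have to be added there. Both bear on the Visit 2 pre-dose SUDS. They hardly touch LSAS, which eligibility requires and which is already in the imputation model.

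A reader might infer three stronger points that the documents do not support:
- *That the SAP contradicts itself by imputing with sex, age and LSAS but not testing with them.* It does not. An imputation model richer than the analysis model is accepted practice and does not show that the authors judged these variables prognostic for the test.
- *That a Visit 3 pre-dose SUDS is the natural covariate because it captures that day's anxiety.* The visible text does not show that such a score is recorded. Adjusting for a post-dose score could remove part of the treatment effect.
- *That the interim conditional power inherits the same imprecision, or that the similar trial's missed endpoint shows imprecision.* The interim model is in a separate interim SAP not available here, and a missed endpoint says nothing about its cause.

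**Conclusion.** The point holds as an efficiency improvement. The primary model uses two adjustment terms while other pre-randomisation values lie unused, so precision may be lost at almost no saving. It cannot be said that precision is lost, because that depends on an R² the documents do not give.

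The balance is asymmetric. With two added covariates the worst case is about 0.4 power points lost from 80%. An added R² of 5 to 10% would gain about 1.6 to 3.6 points, and anything above about 1% is a net gain. These figures assume 18 unpooled sites, complete covariates, and 80% power under the current model; from 90% the gains are smaller (1.1 to 2.5 points).

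**What to change.** Before any unblinding, including the 140-subject look described in Protocol 13.1.6:

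1. Add screening LSAS total score as a covariate in the primary ANCOVA, in SAP 6.1.2 and 8.1.1.
2. Optionally add the Visit 2 pre-dose SUDS. If so, add it to the imputation regression in SAP 6.1.4 and state a rule for missing values.
3. Specify the same model for the interim analysis, and keep the current model as a supportive analysis.
4. Do not use any Visit 3 SUDS score as a covariate.
5. Record the departure from the protocol's stated covariate in SAP 11.

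The cost is 1 or 2 of about 188 degrees of freedom and some SAP wording; no new data are needed. The SAP has to be revised in any case: it was written to protocol Version 3.0, and section 4.2 still says that no interim analysis is planned.

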6.1.3. Multiple Comparisons

[figure not shown]
The type I error rate of $\alpha = 0.05$ will be maintained for the study by using a fixed-sequence testing strategy for the primary and secondary endpoints. Testing of the secondary endpoint will proceed only if the primary endpoint achieves statistical significance. No multiple comparisons adjustments will be made for the exploratory endpoints as the analyses are included for descriptive purposes only. All P values for each comparison will be provided in the summary tables for informational purposes.

The testing will be done in the following order:

1. Primary efficacy endpoint: difference in average SUDS score during the Visit 3 (Treatment) public speaking challenge versus the average SUDS score during the

AD-ST-33.06 Effective date: 12-Nov-2020

Version Final 1.0 | Date 28-Jun-2022 | AD-ST-33.06 Effective date: 12-Nov-2020 | Page 21 of 140

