The analysis for the multiple imputation will match that described for the primary efficacy analysis (Section 8.1.1). Results from the multiply-imputed datasets will be combined using the standard Rubin's rules for multiple imputation (Little and Rubin, 1987) and will be done in SAS using PROC MIANALYZE.

Analysis visits will be assigned based on the nominal visit recorded in the study database.

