6.1.7.2. Subjective Units of Distress Scale (SUDS)

The SUDS, used at Visit 2 (Baseline) and Visit 3 (Treatment) as part of each public speaking challenge, is scored 0 to 100. It is a standard instrument for rating social and performance anxiety in patients with SAD during role-playing situations. Scores are operationalized for subjects in this study as 0=totally relaxed or no anxiety100=most distress or anxiety imaginable.

- Average SUDS Score = Sum of SUDS scores recorded at divided by the number of SUDS scores recorded during the speech performance. For complete data, there should be SUDS scores collected.
- Proportion SUDS Responders = Proportion of subjects with an improvement of 20 or more points in average SUDS scores from Visit 2 (Baseline) to Visit 3 (Treatment).
- Fraction of Missing Change from Baseline in Average SUDS Scores = Number of
 missing values of change from baseline to Visit 3 (Treatment) average SUDS scores
 across all subjects in the ITT Population divided by the total number of expected change
 scores (1 per subject). The fraction of missing change from baseline in average SUDS
 scores is used to compute the threshold for determining whether to implement the
 multiple imputation procedure.

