8.1.2. Complete Case Sensitivity Analysis of the Primary Efficacy Endpoint

If imputation of missing data is required, a complete case analysis will be performed in the ITT population. The complete case analysis will be exactly parallel to the planned primary efficacy analysis, except it will exclude any participants with missing average SUDS scores at Visit 3 (Treatment), using only observed responses. Descriptive summaries will be provided for the primary endpoint based on the complete-case data.

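### With 5% or fewer missing, SAP 8.1.1 fills primary change scores with the arm mean, so the test slightly exceeds 5% type I error: about 5.1% with 1 missing, 6.2% with 10 of 208

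*SAP*

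**What the plan says.** SAP 8.1.1 sets out two routes for a missing primary change score. Above a missing fraction of 0.05 the score is multiply imputed. At 0.05 or below, "missing change from baseline to Visit 3 (Treatment) in average SUDS scores will be imputed with treatment group mean change scores". The same section gives the planning expectation: "It is expected that all randomized study subjects will complete the Visit 3 (Treatment) assessments".

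SAP 6.1.4 describes the route above 0.05, where "multiple imputation of the change from baseline to Visit 3 (Treatment) average SUDS scores will be carried out for the primary efficacy analysis". That method is fully specified: fully conditional specification within arm, five regression variables, 25 datasets and fixed seeds. It also carries the imputation uncertainty: "Results from the multiply-imputed datasets will be combined using the standard" Rubin's rules. SAP 6.1.7.2 says that the missing fraction "is used to compute the threshold for determining whether to implement the" multiple imputation procedure. If a subject has only some of the challenge scores, "then their average SUDS score will be calculated using the non-missing scores", so a change score is missing only when no Visit 3 challenge score exists at all.

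SAP 8.1.2 adds a sensitivity analysis: "If imputation of missing data is required, a complete case analysis will be performed in the ITT population".

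SAP 6.1.3 commits to a study-wide type I error of 0.05 through a fixed sequence: "Testing of the secondary endpoint will proceed only if the primary endpoint achieves statistical significance".

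**The concern.** Replacing a missing value once by the mean of its own arm adds an observation with almost no residual. The arm means hardly move, but the residual variance falls and the apparent sample size rises. The reported standard error is then too small and the test rejects too often.

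This happens in the analysis that decides the trial. The mean-imputed p-value is the primary result and opens the test of the CGI-I endpoint. The complete-case ANCOVA, which has the right size, is only a sensitivity analysis. The plan is also uneven: it propagates imputation uncertainty above 5% missing and ignores it at or below 5%. At stake is a small excess over the 0.05 that SAP 6.1.3 promises, whenever 1 to 10 of 208 randomized subjects give no Visit 3 challenge score.

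**Working it through.** **Inputs.** N = 208, 104 per arm (SAP 3.2); two-sided alpha 0.05 (SAP 4.1); 15 to 18 sites (SAP 3.2), 16 used in the simulations; ANCOVA with treatment, analysis site and baseline average SUDS (SAP 8.1.1). Since 0.05 × 208 = 10.4, the rule covers up to 10 missing (4.8%); 11 missing (5.3%) triggers multiple imputation. The documents do not give the correlation between baseline and change, so 0, -0.4 and -0.7 were tried as assumptions.

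**Formula.** Take two balanced arms with m missing in total and residual variance s².

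- True variance of the treatment difference: 4s²/(N − m).
- Residual variance after filling: about s²(N − m)/N, because the filled values add almost nothing to the residual sum of squares.
- Reported variance: about 4s²(N − m)/N².
- Reported SE / true SE = (N − m)/N = 1 − m/N.
- Actual type I error = 2 × [1 − Φ(1.96 × (1 − m/N))].

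With m = 0 this returns the plan's own 0.05.

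**Results at N = 208.** The simulations used 120,000 null trials per scenario of the SAP's ANCOVA, with Monte Carlo SE 0.06 points. The ranges run over three scenarios: missing completely at random with correlation 0, the same with correlation -0.4, and missingness rising with baseline with correlation -0.4.

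| Missing | 1 − m/208 | Formula | Simulated, mean imputation |
|---|---|---|---|
| 0 | 1.000 | 5.00% | 4.98–5.01% |
| 1 | 0.995 | 5.11% | 5.07–5.12% |
| 2 | 0.990 | 5.22% | 5.20–5.23% |
| 5 | 0.976 | 5.58% | 5.53–5.60% |
| 10 | 0.952 | 6.21% | 6.16–6.20% |

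Complete-case ANCOVA gave 4.93–5.03% throughout. A smaller set of runs (40,000 each, Monte Carlo SE about 0.11 points) gave 5.00%, 5.02% and 5.59% at 1, 2 and 5 missing, and 5.98–6.20% at 10. Complete-case ANCOVA on the same data gave 4.89%, 4.82%, 4.98% and 4.80–5.06%. The paired excess in those runs is thus about 0.1, 0.2, 0.6 and 1.2 points.

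**How firm the top figure is.**

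- An exact t version with about 20 model parameters gives 6.27% at 10 missing. With all 10 in one arm, unrelated to baseline, the two-parameter t version gives 6.24%.
- If the interim analysis in protocol 13.1.6 raises N, the missing fraction can reach exactly 5%: 2 × [1 − Φ(1.96 × 0.95)] is about 6.3%.
- With all 10 missing in one arm and selected toward high baseline, simulated error was 7.1–7.4% at correlation -0.4 and 9.8–10.7% at -0.7. Complete-case ANCOVA gave 4.9–5.2%. Here the arm mean ignores baseline, so the estimate itself shifts, by about 0.7 and 1.2 SUDS points on an SD of 18. The m/N formula does not describe that part.

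**Averaged over how many go missing.** The documents give no rate. If each randomized subject independently has a 0.1%, 0.5%, 1% or 2% chance of no challenge score (assumed), a binomial mixture of the formula values (5.0% above 10 missing) gives an overall type I error of 5.02%, 5.12%, 5.24% or 5.48%. The chance of 10 or more missing is below 0.01% up to a 1% rate and about 1% at 2%.

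**The case against.** The strongest reply is that the rule will hardly ever act. Randomization and the speech fall at the same visit (protocol 10.2.3). Partial scores are averaged. A subject who cannot finish is asked for a score before leaving the room (protocol 10.2.2, applied to Visit 3 by 10.2.3). Randomization follows a completed Visit 2 challenge (SAP 3.5), so baseline should be present. With none missing the effect is exactly zero, and with one it is 0.1 points. Whenever imputation is used, SAP 8.1.2 puts a complete-case analysis in the report, so a result that hinged on the filled values would be visible.

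All of that stands, and it keeps the point minor. It does not remove it. The sentence operates only when the expectation of no missing data fails. Dosing comes twenty minutes before the speech (protocol 9.2), so a randomized subject can leave before any challenge score exists and still belong to the ITT population. A visible discrepancy in a sensitivity table does not change which p-value opens the sequence.

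A reader might go further and infer one of three things that the documents do not support:

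- That the trial runs at about 6%. That needs 10 missing, and the SAP expects none.
- That SAP 6.1.4 and 8.1.1 contradict each other because 6.1.4 visibly covers only the route above 0.05. Text is missing from the public copy of 6.1.4, so this cannot be claimed.
- That every mean-imputed p-value is too small. The direction holds on average only: at 10 missing, 1.2–1.5% of null trials gained significance relative to complete cases and 0.03–0.3% lost it.

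**Conclusion.** The concern holds, at minor severity. As written, the primary test is slightly anti-conservative whenever at least one but no more than 5% of change scores are missing. If missingness is unrelated to arm, the error runs from about 5.1% with 1 missing to about 6.2% with 10 of 208, or about 6.3% at exactly 5% missing with a larger N.

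It is tempting to read 6.2% as a ceiling, but it is not one. Missingness that depends on both arm and baseline adds bias and pushed the error to about 7% to 11% in contrived cases that are very unlikely in this design. None of the figures covers missingness that depends on the unseen Visit 3 score. The residual SD does not affect the error rates. The baseline correlations and the per-subject missing rates are assumptions.

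**What to change.** Delete the mean-imputation sentence in SAP 8.1.1 and, at 5% or less missing, name one of these as primary:

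- **Observed-case ANCOVA**, as already specified in SAP 8.1.2. It is the simpler repair, because only the outcome is missing and site and baseline are already in the model. It stayed near 5% in every scenario above, including selection on arm and baseline. It needs the trigger in 8.1.2 reworded, since that depends on imputation being required. It also needs an entry in SAP section 11, because protocol 13.1.4.6.4 calls for imputation when Visit 3 scores are missing.
- **The multiple imputation of SAP 6.1.4 at any non-zero missing fraction**, with 8.1.2 kept as the sensitivity analysis. This agrees with protocol 13.1.4.6.4 and leaves Tables 14.2.1.1 and 14.2.1.2 as planned. Simulated type I error (25,000 trials, missing completely at random, correlation -0.4) was 4.9% at 1 to 5 missing and 4.7% at 10, with Monte Carlo SE 0.14 points. One caution: imputing within arm with site in the model may be fragile when an analysis site holds only 6 subjects (SAP 6.1.6), about 3 per arm. The simulations used 13 per site and did not test this.

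In either case, align the threshold wording in SAP 6.1.4 and 6.1.7.2 after checking the unredacted text.

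The cost is a few sentences and a slightly larger standard error than mean imputation reports:

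| Missing | Observed-case | Multiple imputation |
|---|---|---|
| 1 | +0.4–0.5% | +0.6% |
| 2 | +0.8–1.0% | +1.2% |
| 5 | +2.1–2.6% | +3.0% |
| 10 | +4.5–5.3% | +6.2% |
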